11.6 Deaths, Serious Adverse Events and other Significant Adverse Events

A serious adverse event (SAE) is defined as any untoward medical occurrence that at any dose: results in death, is life threatening, requires inpatient hospitalization or prolongation of existing hospitalization, results in persistent or significant disability/incapacity or is a congenital anomaly/birth defect.

Expected SAE and responses to these events include:

- 1) **Disclosure of intent to self-harm or harm others and/or disclosure of child abuse.** Teens will also be questioned about depression/self-harm on the K-SADS-PL interview. Consistent with procedures established in several ongoing studies at the Center for ADHD, we will follow a formal process to identify, document, and manage risky behaviors. All K-SADS-PL interviewers will be responsible for identifying and reporting whether the teen is experiencing suicidal ideation or is currently being abused/neglected. If any risk is identified during the K-SADS-PL interview, the interviewer will page the PI or other co-Is to discuss the situation and determine what additional information is necessary to ascertain risk and engage in safety planning, including considering hospitalization, CPS reporting, etc. Teens will be notified at the beginning of the interview (and in the assent form) that anything they discuss during the interview will be kept confidential except if they report any behaviors that place themselves at risk; in those cases, their parents will be informed on the day of the interview and will be part of safety planning. A critical items checklist will be completed

immediately after the interview. Any safety plans will be documented on the critical items checklist.

11.7 Prior and Concurrent Medications

A medication interview conducted with the teen and parent that captures current prescribed medication usage and past prescribed medication usage for attention, learning, emotional, or behavioral difficulties since driving. This questionnaire will be administered during the in-person visits at Baseline and 6-months. In addition, this questionnaire will be sent as a REDCap survey for teens to complete at the 12-month time point.

The summary statistics for who was taking stimulant medication at baseline and during the 1-year of naturalistic driving for the whole sample and separately for each intervention will be produced.

12 Reporting Conventions

P-values ≥ 0.001 will be reported to 3 decimal places; p-values less than 0.001 will be reported as “<0.001”.

13 Quality Assurance of Statistical Programming

All primary analyses will be performed in SPSS (version 27) and SAS (version 9.4) using the generalized linear model function. All secondary analyses will be performed using *Mplus* (version 8.8) and SAS (version 9.4) on a Windows operating system. All analyses will be performed by [name]. All analyses code and results will be double-checked by [name].

14 Summary of Changes to the Protocol and/or SAP

The changes from the protocol-specified definitions of aims, outcomes and statistical analytic approaches are outlined below. Changes to the study procedures are also included here. These changes reflect 1) budget cuts that impacted our study design and 2) advances in our knowledge and experience with research methods in recruiting adolescents with ADHD, driving, and human factors.

14.5 Aims Changes

None.

14.6 Outcomes Changes

5/9/2016

- 1) **No longer collecting and coding randomly selected clips from low threshold events collected from DriveCam technology.** Initially, we were informed that the DriveCam would have a “canary” feature that would randomly record events irrespective of the g-force thresholds. These events would allow us to assess eye-glance behavior that was not tied to g-force events. The “canary” feature did not work with the DriveCams we purchased. Hence, we set the threshold for g-force events at a lower level (i.e., $>.45$ g-force) than the planned $>.6$ g-force threshold that would be used for defining events. However, this lower threshold began to produce so many events among our randomized participants that our

servers could not keep up with the number of videos produced. Moreover, the coding demand was too great and unmanageable. It was decided by the research team on 3/26/19 to modify the g-force thresholds back to $>.6$ g-force and to only save and code those events.

6/1/2016

- 1) We received our notice of grant award for grant #R01HD084430. The proposed budget was cut by approximately 17%. We needed to modify the scope of some of the proposed work to accommodate the 17% budget reduction. The following outcomes and assessment changes were approved by our NICHD program officer:
 - a. Due to the reductions in effort to the investigators and staff and to reduce subject payment costs, we reduced the number of outcome assessments we had originally proposed. The original application proposed collection of baseline, 1-month, 4-month, 8-month, and 1-year post-randomization assessments. We now propose to conduct in-person assessments at baseline, 1-month, and 6-month post-training.
 - b. We also made changes to the types of assessments we will include in the study. We will no longer include a road-test assessment. Excluding the road test still allows us to assess driving performance using our remaining three driving measures. That is, use of driving simulation, DriveCam monitoring, and driving records will allow us to assess teen's driving behavior. Hence, we feel that even in the absence of the road test, we will continue to possess the scope of driving assessment necessary to detect between-group differences on driving outcomes.
 - c. Due to the cost, the MEMSCap Medication Event Monitoring System was dropped from the study protocol. We replaced daily monitoring of ADHD medication use using self-reported measure of medication administered at baseline and each follow-up visit.

10/30/2019

- 1) **Increase in sample size based on attrition for 6-month driving simulator visit.** Our initial protocol proposed to randomize 136 participants; however, this randomization goal was based on successfully collected data from 136 at the 1- and 6-month driving simulations—the source of our primary endpoints. When we reached 136 recruited participants, we have estimated a new attrition rate based on data collected thus far. This calculation suggests that we need to over-recruit to a randomized sample size of 152 to achieve 136 participants with 1- and 6-month simulator outcomes (primary endpoints).

1/11/21

- 1) **BMV records no longer an outcome of interest.** Once all BMV records were collected, we examined the frequency of BMV-reported MVCs. We also compared these rates to the frequency of behaviorally coded MVCs captured by DriveCam technology. The frequency of MVCs according to BMV records was 19 total MVCs across the entire sample over the course of 1-year of driving. According to DriveCam codings of collisions, there were >100 crashes across the entire sample over the course of 1-year of driving. Thus, the research team decided that BMV crashes were not an accurate outcome measure and therefore it would no longer be used as an outcome measure.

14.7 Statistical Changes

6/1/2016

- 1) **Changes were made to the protocol to reduce the budget with one having implications for the statistical analysis (See Protocol Changes 6/1/2016).** Specifically, the MEMSCap Medication Event Monitoring System would have allowed us to continuously track daily use of medications during the study period. This measurement of medication was being replaced with an administration of self-reported measure of medication use. This measure asks about medication use over the 6 months rather than daily use. Thus, we cannot meaningfully include medication status as a time-varying covariate in analyses as originally intended.

12/1/2016

- 1) **Changes were made to the protocol to address subject burden which caused us to reconsider the statistical approach (See Protocol Changes 12/1/2016).** In particular, rather than having a single 30-minute run of driving simulator data, we had two 15-minute runs. We made a decision to compute driving simulation outcomes for each run and then include run in the model. Hence, run would be nested within assessment time point (baseline, 1-month, & 6-month) and would create a double repeated measure (i.e., 2 driving “runs” nested within 3 repeated measurements). Generalized linear equations (GEE) handle double repeated measure data better than the originally proposed ANCOVA analysis. In addition, GEE models a) provide a more stringent test of significance; b) are more amenable to analyzing binary and count outcomes; c) and use a long database format which allows us flexibility in handling missing data. Hence, we modified our statistical approach to use GEE rather than ANCOVA models.

Further, statistical models for examining intervention effects on DriveCam outcomes were modified to allow us to use multilevel mixed longitudinal linear models. Specifically, each participant will have repeated measures response variable data collected over time (i.e., level 1), and within each participant, these responses are not independent but correlated. However, the interest is between-participant variation (level 2) as explained by random assignment. This means within-participant (level-1) variation is not of interest to answering the treatment effect research question, but such variation must be either modeled or controlled appropriately to avoid Type-1 inferential errors. To do so, participant will be declared as the level 2 clustering variable, and specific commands in Mplus (‘Type = Complex’) will be used to: 1) estimate the intra-class correlation (ICC), which quantifies the non-independence of response variable data, 2) compute the design effect ($= C - 1 * ICC$), which is the multiplier needed to be applied to standard error estimates to avoid Type-1 errors, and 3) test the effect of randomization on binary indicators of crash/near-crashes (1=yes, 0=no) and presence of 2-second off-road glances (1=yes, 0=no). Further, it is well-known that analytic techniques such as ‘Type=Complex;’ will only accurately correct parameter estimate standard errors if the number of clusters at level 2 is greater than 20. By declaring participant as the level 2 clustering unit, and N (or, in this case, C), which is more than sufficient to accurately correct standard errors to obtain an accurate treatment effect estimate.

06/23/2022

The following statistical changes were made based on New England Journal of Medicine reviewer, statistical expert, and editor feedback.

- 1) **Changes to primary analyses.**
 - a. **Reporting adjusted mean differences for Standard Deviation of Lane Position.** Reviewers noted that we should report adjusted mean differences rather than raw mean differences for standard deviation of lane position at 1-month and 6-months post-training.

b. Reporting exponentiated incidence rate ratio for comparing group differences in eye glance data. We now report exponentiated incidence risk ratio for count of long glances during driving simulation. We computed an exponentiated incidence rate ratio which is the appropriate statistic for comparing two counts.

c. Change in correction for type I error. We initially proposed to use false discovery rate to control for type I error. However, the statistical expert reviewer indicated that Bonferroni corrected alpha is more a more appropriate type I error control in confirmatory studies of a small number of pre-specified hypotheses. Accordingly, we used a Bonferroni corrected alpha threshold of 0.0125 for assessing statistical significance of the four primary outcome measures at 1-month and 6-months.

d. Change in covariate. Rather than use years since licensure as a covariate, we now use months of driving experience instead of years of experience in all our analyses.

e. Change in handling of missing data. Multiple imputation was used (See 8.4 Missing Data for more details) to handle missing data rather than maximum likelihood estimation.

2) Addition of supplemental analyses.

a. Sensitivity analysis of naturalistic driving results including only teens whose 1-year of naturalistic driving ended prior to COVID restrictions. Of the 152 participants, 56 (FOCAL+: n=29 teens; Sham Control: n=27 teens) participants had a portion of their 1-year of naturalistic driving that included days beyond March 15, 2020, when COVID restrictions were put into place. We conducted a sensitivity analysis of our naturalistic driving results including only the 96 teens (FOCAL+ n=47; Sham Control n=49) whose 1-year of naturalistic driving ended prior to COVID restrictions.

b. Moderator analyses. We ran a moderator analysis examining age and medication status as moderators of FOCAL+ training effects. For the driving simulation outcomes, we examined whether the improvements from baseline to 1-month post-training and baseline to 6-months post-training were moderated by baseline age or medication status. We ran GEE models like those conducted for the primary analyses as described in 10.1 Primary Analysis, however we inserted the moderator variable in the model, analyzed a fully factorially crossed 4-way interaction model, but assessed the significance of the relevant 3-way interactions (Group x Drive Timepoint: baseline vs. 1-month; baseline vs. 6-months x [Moderator Variable]). For DriveCam outcomes, we examined whether group differences on long glances and crash/near-crashes were moderated by baseline age or medication status. We ran multi-level generalized linear mixed models with a logit link function similar to those conducted for the secondary analyses as reported in the manuscript, however we inserted the moderator variable in the model and assessed the significance of the 2-way interaction between Group x [Moderator Variable].

08/15/2022

The following statistical changes were made based on New England Journal of Medicine statistical expert and editor feedback.

1) Supplemental analyses were trimmed to analyses for which we could provide a strong rationale. Specifically, we will only report moderation analysis of the medication on training outcomes and COVID-19 sensitivity analyses.

a. Medication Moderation. For the driving simulation outcomes, we examined whether the improvements from baseline to 1-month post-training and baseline to 6-months post-training were moderated by medication status. These analyses were not intent-to-treat since only the 140 teens for whom we had information about medication status during the 1 year of follow-up were included in these analyses. Adjusted mean differences for standard-deviation of lane-position and natural logarithmic incident rate ratios for count of long glances were computed

using multiple group analysis methods. Specifically, conditional on months of driving experience, training group difference statistics were computed separately across binary medication status.

For DriveCam outcomes, relative risk statistics for binary indicators of long glances and crash/near crash were computed conditional on both months of driving experience and days of DriveCam installation. Specifically, relative risk statistics were computed separately across binary medication status

b. COVID-19 Sensitivity. For 56 (FOCAL+: n=29 teens; Control: n=27 teens) of the 152 participants, their 1-year of naturalistic driving included days beyond March 15, 2020 when COVID restrictions were put into place. We conducted a sensitivity analyses of our naturalistic driving results by re-running our primary and secondary analyses but including only the 96 teens (FOCAL+ n=47; Control n=49) whose 1-year of naturalistic driving ended prior to COVID restrictions.

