There have been multiple calls for the development and testing of driving interventions that target teens at the highest risk for MVCs^{29, 30} with increased recognition that some subgroups require additional strategies over and above strategies used for typical teens (e.g., graduated driver licensing)²⁹. Given the incremental risk of an ADHD diagnosis on driving outcomes, especially among teen drivers, there is a clear and urgent need for driving interventions for teens with ADHD⁵⁴. While ADHD medications, especially stimulants, are effective at remediating ADHD-related driving impairments⁵⁴⁻⁵⁶, medications are only effective when they are taken and during the period of pharmacological effect. *Yet teens present with distinct temporal patterns in driving and MVCs that both peak during after-school late afternoons and evenings^{8, 10-12} when stimulant medication effects are waning^{57, 58}*. The few non-pharmacological interventions that have been evaluated for resolving ADHD-related driving deficits target teen-parent interaction and hazard detection^{54, 59}. Recent reviews of this ADHD driving intervention literature have emphasized that future development of driving interventions for teens with ADHD must be tailored to address the mechanisms contributing to ADHD driving deficits^{29, 30, 54}. To date, no driving intervention studies for ADHD drivers have targeted visual attention while driving, which according to our data (see Preliminary Studies) is a key mechanism in driving deficits among teens with ADHD²⁸.

3.e Parallels between ADHD driving deficits and ADHD neurocognitive deficits

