Behavior Rating Inventory of Executive Function: (BRIEF)⁹¹: There are separate parent- and self-report versions of this questionnaire which assess executive functioning in teens. Scale scores include various aspects of executive functioning (e.g., Inhibit, Emotional Control, Working Memory, and Monitor). Baseline scores on executive functioning will be evaluated as potential moderators of treatment response.

Pittsburgh Sleep Quality Index (PSQI)⁹²: The PSQI is a self-rated questionnaire which assesses sleep quality and disturbances. Several aspects of sleep are assessed by this scale including sleep latency, duration, sleep disturbances, use of sleeping medication, and subjective sleep quality. We will evaluate sleep quality and quantity as a potential covariate in our outcome analyses.

Services Use in Children and Adolescents-Parent Interview (SCA-PI); Service Barriers and Attitudes⁹³: This brief structured interview conducted with the parent captures adolescent services use across mental health, primary care, school, and community settings. Medication use data acquired from this interview will be entered as a covariate into our statistical modeling.

Consumer satisfaction questionnaire: Teens and parents will complete a consumer satisfaction questionnaire asking them about their own opinions of the intervention. Questions will focus on the following domains: 1) appreciation of intervention format including length, setting, computer interface, etc.; 2) perceptions of whether they felt that the intervention might help them drive better; and 3) whether they would recommend this intervention to other teens.

Driving simulation (primary outcome measure): *In addition to testing at baseline and each of the major assessment points, a driving simulation assessment will also occur for participants in both intervention groups immediately preceding each of the weekly training sessions. This will allow an examination of the number of weekly training sessions that are needed to reduce extended glances away from the roadway to levels seen among experienced drivers. Note that in order to reduce overlap between the FOCAL+ simulator training and simulator assessments, the driving scenarios will differ across these two situations.*

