In addition, since we will NOT be asking teens to terminate medication during this naturalistic assessment of driving, we will need to record information about ADHD medication use including medication type and dosage. Families will be queried about ADHD medication prescriptions at each clinic assessment using the SCA-PI interview (see above). Further, families will use a medication event monitoring system (MEMSCAP™) over the course of the year to electronically track date and time of medication administration.

Review of driving records: Participants' driving records from the Bureau of Motor Vehicles dating back from licensure and extending until 1-year post randomization will be obtained. We will record the number and type of traffic violations, incidents of driving while intoxicated, license suspensions and revocations, and MVCs.

Table 1: Schedule of measures

Measure	Done By	Purpose	Time to complete	Screening/ Baseline	Post-Randomization			
					4-week training	1-, 4- 8-, and 12 month assessments		
K-SADS	A,P	IN,M	90 m	X				
VAPRS	P,T	M	5 m	X				
Conners-3 Self-Report	A	M	5 m	X				
WASI-II	A	IN,M	30 m	X				
Driving Ability Quest.	A	M	10 m	X				
Temporal Reproduction	A	M	15 m	X				
Go/No-go task	A	M	30 m	X				
BRIEF	A, P	M	10 m	X				
PSQI	A	M,C	10 m	X		X	X	X
SCA-PI	P	C	20 m	X		X	X	X
Driving Simulator	A	M,O	30 m	X	WEEKLY	X	X	X
Road Test	A	M,O	20 m	X	1st SESSION	X	X	X
DriveCam	A	M,O	N/A	X	← CONTINUOUS →			
Driving Records	N/A	O	N/A	X	← X			
Consumer Satisfaction	A	S	5 m			X	X	X

Notes: A=Adolescent; P=Parent; T=Teacher; IN=inclusion measure; M=moderator measure; C=covariate measure; O=outcome measure; S=Satisfaction measure

Note about driving measures: Four different driving outcomes will be utilized for assessing driving performance. There are trade-offs for each measure in terms of its use during training (e.g., raising concerns about training to the task), whether the driving environment can be controlled (e.g., assigning distracting secondary tasks), whether eye glance behavior can be measured during driving, and each tasks ecological validity. These trade-offs are outlined in Table 2. No single measure is ideal. However, by including all four measures, we feel that we are comprehensively assessing driver's visual behavior and driving performance.

Table 2: Driving measure trade-offs

	Not used during training	Can control environment	Able to measure eye glances	Ecologically valid
Simulator		X	X	
Road test	X	X	X	
DriveCam	X		X	X
Driving records	X			X

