The hypotheses listed above will use the same statistical modeling. For each analysis, every randomized teen will be kept in the analyses (i.e., intent-to-treat approach). Mixed factorial ANCOVAs will be used to analyze the data. The two independent variables in the analyses will be Intervention (FOCAL+ vs. Sham Intervention) and Time (immediately after initial training, and 1-, 4-, 8- and 12-months post- randomization). Months of driving experience will be covaried. To test Hypotheses 1, the primary dependent variable will be the number of extended (>2 sec) glances away from the roadway during driving simulation. Secondary analyses testing Hypotheses 1 will focus on other visual attention outcomes across the intervention groups including number of extended glances away from the roadway during the road test.

To test Hypotheses 2, the primary dependent variable will be SDLP during driving simulation. Secondary outcomes for Hypotheses 2 include 1) number of MVCs and reaction time to unexpected events during driving simulation, 2) number of lane crossings and proportion of time out of lane during the road test, 3) number of incidents, near-crashes, and crashes per hour during DriveCam monitoring; and 4) rates of MVCs from teen's driving records. When examining DriveCam outcomes, we will add a time-varying covariate indicating medication use to account for the effects of medications on driving outcomes.

For each statistical model, the term of interest is the main effect of Intervention. A significant main effect of Intervention would indicate that the FOCAL+ intervention significantly impacted eye glance and driving outcomes. A significant Intervention effect will be followed up with post-hoc comparisons to determine the direction and locus of the effect, including whether intervention effects were maintained at 4-, 8-and 12-months post-training. Though we expect intervention effects to be strongest immediately following training (1-month), we predict that FOCAL+ will be more effective than the sham intervention for ADHD teens at each time point.

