8.3 Covariates and Subgroups

For all analyses:

- Driving experience: Defined as baseline date minus the date that the teen received their graduated or full unrestricted license. Computed in months.

Specific to driving simulation analyses:

- Driving runs: Included in order to be able to include primary outcomes from the two driving runs conducted at the baseline, 1-month post-training assessment, and the 6-month post-training assessment. Generalized estimating equation (GEE) analyses allowed driving simulation data from the two "runs" nested within each of the three "drive types" nested within each participant to be modeled as correlated response variable data, but main or interaction effects for "runs" were not of theoretical interest.

Specific to DriveCam analyses:

- To account for variability in the length of time the DriveCam camera was installed in each participants' automobile during the 1-year post-training period was included as a covariate in addition to months of driving experience as detailed above.

Supplemental Analyses (Requested by New England Journal of Medicine reviewers, editor, and/or statistical expert)

- Moderation Effects—These analyses are post-hoc; thus, effects (adjusted mean difference or relative risk and 95% CI) will be reported rather than significance testing. Note that the widths of confidence intervals are not adjusted for multiple comparisons and no definite conclusions can be drawn from these results.

- Medication status dichotomized based on whether the teen reported taking ADHD medication at any point during the 12-months of naturalistic driving.
- COVID-19 Sensitivity Analysis
 - For 56 (FOCAL+: n=29 teens; Control: n=27 teens) of the 152 participants, their 1-year of naturalistic driving included days beyond March 15, 2020 when COVID restrictions were put into place. We will conduct a sensitivity analyses of our naturalistic driving results by re-running our primary and secondary analyses but including only the 96 teens (FOCAL+ n=47; Control n=49) whose 1-year of naturalistic driving ended prior to COVID restrictions.

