9.8 Demographic and Baseline Variables

The data set will be summarized by treatment groups with respect to important confounders. The distributions of categorical variables will be tabulated by treatment group and overall. Continuous variables will be summarized as mean, median, and standard deviation by treatment group and for the overall sample.

- Age in years
- Age at licensure
- State of licensure
- Gender
- Race
- Ethnicity (Latino/a; Not Latino/a; Unknown)

Trial of Training to Reduce Driver Inattention in Teens with ADHD

- Maternal/Paternal education (highest level)
- Family income
- License Type (Graduated driver’s license; full unrestricted license)
- Driving experience (calculated as months since licensed)
- Full Scale IQ
- Number on stimulant medication at baseline
- Number on stimulant medication during 1-year of post-training driving
- VAPRS scores (Inattention, Hyperactivity/Impulsivity, and Total Score)
- K-SADS ODD diagnosis
- K-SADS Anxiety Disorder diagnosis
- K-SADS Mood Disorder diagnosis

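### The main DriveCam models have no ADHD medication term, although baseline use is recorded before randomisation and the SAP's stated reason rules out only a time-varying covariate

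*Combined protocol and SAP*

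**What the plan says.** **Role of medication.** Protocol section 3.d states that "ADHD medications, especially stimulants, are effective at remediating ADHD-related driving impairments". Simulator visits are held off stimulants (SAP 6.1, 6.2). DriveCam driving is not: protocol 5.e.1 says medication must be recorded "since we will NOT be asking teens to terminate medication during this naturalistic assessment of driving".

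**The protocol's plan.** There were two separate commitments. For DriveCam outcomes, section 5.f.2.a said "we will add a time-varying covariate indicating medication use to account for the effects of medications on driving outcomes". For the parent interview on service use, section 5.e.1 said "Medication use data acquired from this interview will be entered as a covariate into our statistical modeling". The second did not depend on electronic monitoring.

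**The change.** SAP 14.6 (6/1/2016) records the loss of the monitoring device: "We replaced daily monitoring of ADHD medication use using self-reported measure of medication administered at baseline and each follow-up visit". SAP 14.7, same date, draws the consequence: "Thus, we cannot meaningfully include medication status as a time-varying covariate in analyses as originally intended".

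**The current models.** For DriveCam, SAP 8.3 says that camera-installation time "during the 1-year post-training period was included as a covariate in addition to months of driving experience as detailed above". The long-glance imputation model in 8.4 uses the same two covariates, and 10.6 adds none.

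**Where medication does appear.** Section 9.8 lists "Number on stimulant medication at baseline" among the variables summarised by arm, and 11.7 repeats the summary for baseline and for the follow-up year. Section 8.3 and the 08/15/2022 entry in 14.7 specify a supplemental analysis that gives DriveCam relative risks separately by medication status, defined as any reported use during the 12 months of naturalistic driving.

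**The concern.** Both secondary endpoints come from a year of driving under whatever medication each teen takes, and the protocol itself names medication as something that improves ADHD driving. The plan to adjust for it ended for a reason that covers only daily, time-varying data. A fixed baseline term needs no daily data, and the SAP does not say why one was not used.

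Two design features make the gap more relevant than usual:

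- Medication is not a stratification factor. Protocol 6.a stratifies by gender and driving experience; SAP 6.3 describes only blocks of 10.
- SAP 8.4 calls the DriveCam analysis non-intention-to-treat, and 6.4 leaves out teens without a triggered event. Having an event is itself a post-randomisation outcome, so the balance given by randomisation is not assured in the analysed set.

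At stake is how far a chance difference in medication use moves two relative risks, and whether a recorded predictor is used to tighten their intervals.

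**Working it through.** The documents state no sample size, power or adjusted estimate for the DriveCam endpoints, so there is no figure of the plan's own to reproduce. The check has two parts.

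**1. Is a usable baseline variable available?**

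- SAP 6.1 (Study Timeline) collects medication use at baseline, 6 months and 12 months; 11.7 says the baseline interview is in person.
- SAP 6.4 puts the baseline visit at day -14 to -7 and randomisation at day 0. The variable therefore precedes allocation.
- The follow-up variable differs in kind. It is measured after allocation, and it is known for 140 of 152 teens (stated under the simulator moderation analysis in 14.7), so 12/152 = 7.9% are missing.

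**2. How large could the effect of the omission be?**

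From the documents: teens per arm, from the COVID counts in 8.3, are 29 + 47 = 76 (FOCAL+) and 27 + 49 = 76 (control).

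Assumed, because the documents give no figure: share medicated p = 0.3 to 0.7; per-event risk ratio for medication r = 0.5 to 0.85; SD of the log rate between teens, tau = 0.8 to 1.2.

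*Chance imbalance.* SD = sqrt(2p(1-p)/76).

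- p = 0.5: sqrt(0.50/76) = 0.081; 1.96 x 0.081 = 0.159
- p = 0.3 or 0.7: sqrt(0.42/76) = 0.074; 1.96 x 0.074 = 0.145

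*Shift in the unadjusted relative risk when training has no effect.* With shares a and b medicated in the two arms, RR = (1-(1-r)a)/(1-(1-r)b). At p = 0.5 and 1.96 SD, a = 0.58 and b = 0.42.

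| Share medicated | r = 0.5 | r = 0.7 | r = 0.85 |
|---|---|---|---|
| 0.3 | 0.918 | 0.953 | 0.977 |
| 0.5 | 0.899 | 0.945 | 0.975 |
| 0.7 | 0.894 | 0.946 | 0.976 |

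These are shifts of about 2% to 11% from 1.00. With the imbalance reversed, the factors are the reciprocals, 1/0.977 = 1.02 to 1/0.894 = 1.12. At a more typical 1-SD imbalance they run from 0.988 to 0.944, or about 1% to 6%.

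The figure of 76 per arm is an upper bound for DriveCam, since teens without events drop out. The true spread is somewhat wider.

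*Precision.* R² = p(1-p)(ln r)²/tau², and the standard error is multiplied by sqrt(1-R²).

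- Largest gain (p = 0.5, r = 0.5, tau = 0.8): R² = 0.25 x 0.480/0.64 = 0.188, factor 0.901
- Smallest gain (p = 0.3, r = 0.85, tau = 1.2): R² = 0.21 x 0.0264/1.44 = 0.004, factor 0.998

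The standard error would fall by about 0.2% to 10%.

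**The case against.** **The SAP does not ignore medication in the DriveCam data.** A reader might infer from 14.7 that medication was removed from every DriveCam analysis. The documents do not support that. Section 8.3 and the 2022 entries in 14.7 give relative risks by medication status, and 9.8 and 11.7 would show an imbalance. This stands. But the supplemental analysis is post hoc, splits on a variable that training could in principle affect, and gives stratum-specific estimates without adjusting the main relative risk.

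**There is no bias to remove.** A reader might also infer that the DriveCam comparison is confounded by medication. Under 1:1 randomisation, chance imbalance is part of the sampling error that the 95% interval already expresses. This largely stands. The one qualification is the restriction to teens with events, which weakens the protection of randomisation to an unknown degree.

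**The risk ratios are unanchored.** Both endpoints are risks per triggered event (5.2, 10.6). The protocol speaks of driving impairment in general; medication might instead reduce the number of events, which these endpoints do not measure. This stands, and the larger shifts above also need a tail imbalance.

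**A baseline yes/no is a weak proxy.** SAP 6.1 notes that most teens drive when medication may not be active and that weekend and summer breaks are common. It would be wrong to describe DriveCam driving as uniformly on medication. This stands as a limit on the gain, not as a reason against the term.

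**The departure from the protocol was disclosed.** A difference from superseded text is not an error. The point rests on the current 8.3, 8.4 and 10.6, and on the fact that the recorded reason covers only one form of the covariate.

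**The stakes are modest.** The endpoints are secondary, reported without significance tests and with an explicit caution about conclusions. This stands.

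**Conclusion.** The point holds in a limited form. The main DriveCam GEE models and the long-glance imputation model have no medication term. The recorded reason excludes only a time-varying one, and a baseline measure that precedes randomisation is already collected. The supplemental analysis by follow-up use does not take its place.

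The gain from adjustment is precision and protection against chance imbalance, not removal of systematic confounding. Under the assumptions shown, a 1.96-SD imbalance moves the relative risk by roughly 2–11%, and adjustment trims the standard error by about 0.2–10%. Both ranges depend on an assumed share medicated and an assumed effect of medication on risk per event; if medication does not alter that risk, the gain is nil. This is an inexpensive improvement worth making to secondary, untested endpoints. It gives no ground for calling the DriveCam results invalid.

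**What to change.** - In SAP 8.3 and 10.6, add ADHD medication use at baseline (yes/no, from the baseline medication interview) as a fixed covariate in the GEE models for long glance and for crash/near crash.
- In 8.4, add the same term to the long-glance imputation model, so that imputation and analysis agree.
- State the definition. Section 9.8 counts stimulant use, while 9.6 defines its status variable by ADHD medication; the covariate should name one.
- Do not adjust the main relative risks for follow-up medication status.
- If the main model is considered locked, as the 2022 entries suggest, report the adjusted model as a labelled sensitivity analysis beside the unadjusted result.
- Leave the dated 6/1/2016 entry in 14.7 as it is and add a new change entry recording the covariate and its timing.

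The cost is one sentence in each section and one extra model term, using data already collected. At this stage the analysis has to be labelled as added after the main models were run.
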